6.0 Procedures Involved

Describe and explain the study design.

The study uses a between-subjects experimental design. Participants will be randomly assigned to one of two conditions: experimental vs. control.

Research procedures, including procedures being performed to monitor subjects for safety or minimize risks.

The study involves two parts: a pre-session online baseline survey and an experimental session that will take place in the lab. Trained research assistants will guide participants through study procedures in the lab, including delivery of the intervention (manipulation), assessment of study outcomes, and study debriefing.

As identified in our pilot data and previous research,^{5,7-9,46,113} employment is a common setting for weight discrimination. Negative employment outcomes (e.g., lower wages, fewer opportunities for promotion) often stem from negative stereotypes that cast employees with obesity as lazy, unintelligent, and incompetent.^{5,8} To manipulate weight discrimination, this study will adapt manipulations widely used in previous experimental studies of social exclusion (conducted by Co-I [name])^{50,112} and weight stigma,⁴¹ as well as our own pilot work.⁴⁸

The study will be presented as an investigation of "decision making in the workplace," during which participants (adults with obesity) will "interact with" and receive initial impression ratings from three "co-workers" ("confederates," that is, research assistants posing as other participants). Participants will be told that the research team has partnered with the FSU marketing department to study how psychological factors affect decision making and that during the lab session they will work with their groupmates to develop a food product marketing campaign.

To begin, participants will create a 3-minute introductory "getting to know you" (GTKY) video, as in our pilot study.⁴⁸ To guide the creation of their video, participants will be provided with a list of "getting to know you" questions (please see attached video introduction questions) they can answer in their video. Participants will also complete a "getting to know you" questionnaire in which they will be asked to indicate their personal qualities (filler questions that assess self-monitoring practices) and social values where they will be asked to rate their attitudes toward elderly adults, overweight people, and

PROTOCOL TITLE: Decision Making Study

racial and ethnic minority individuals. Participants' videos and "getting to know you" questionnaire responses (averaged across the three members) will (ostensibly) be shown to their group members, and participants will view three similar videos created (ostensibly) by each of their group members. (Please see two sample confederate videos that were uploaded to IRB staff member [name]'s NiFTy account). After watching the videos, participants will provide impression ratings of each group member.

Participants will also be informed that, for the next portion of the session, the group will be divided into pairs to perform a taste-test task and develop ideas for the marketing campaign. Pairs will (ostensibly) be based on each person's preferences for whom they most want to work with based on the initial videos, and participants will be asked to indicate their preferences. The experimenter will say the following:

"For the marketing task we want to partner people with someone they'd like to work with. Things work better that way. So please indicate here on this paper (at the bottom of the 'First Impressions Questionnaire' page 2) which one of your group mates (A, B, or C) you would most like to work with so we can try to partner you with them."

As described in Section 5.0 (Study Intervention), participants will be randomly assigned to one of two manipulations. In the experimental (weight discrimination) condition, participants will learn that their group members are biased against overweight people but not elderly or racial/ethnic minority individuals, as indicated by the GTKY summary ratings handout in which the three member's ratings will be presented in averaged form (experimental condition). Participants will also receive negative feedback about their personal attributes by being labeled with negative weight-based stereotypes (as indicated by the first impressions summary ratings averaged across the three members; experimental condition). Although some ratings will be positive (e.g., they will receive high ratings on being friendly and kind), participants will be rated poorly on attributes viewed as necessary to develop a strong marketing campaign (i.e., motivation to work hard, possessing self-discipline to persist at the task, and competence).

In the control condition, participants will learn that their group members have positive attitudes toward people with higher body weight, as well as elderly and racial/ethnic minority individuals, as indicated by the GTKY summary ratings handout (control condition). Participants will also receive positive feedback about their personal attributes, as indicated by the summary ratings averaged across the three members (control condition).

After (ostensibly) assembling the group's preferences, the experimenter will inform participants in the experimental condition that no one selected them to be their partner, thus they will perform the next few tasks alone. This manipulation has been shown to prompt feelings of social exclusion.⁵⁰ In contrast, participants in the control condition will be told that one of their group members had to leave unexpectedly for a family emergency, so pairs cannot be assembled as usual, thus they will perform the next few tasks alone. In sum, while participants in both conditions will perform the tasks alone, only those in the experimental condition should experience social exclusion. For the exact wording of the social exclusion manipulation, please see the attached script (social exclusion manipulation).

PROTOCOL TITLE: Decision Making Study

After the manipulation has been delivered, participants will complete a manipulation check (see lab survey). Participants will be asked to indicate their overall impressions of their groupmates and their perception of their groupmates' overall impressions of themselves. Participants will be also report the extent to which they think the impressions their group members formed of them thus far are based on various factors including their gender, race or ethnicity, weight, age, personality, and what they said in their video.⁴⁸

Next, participants will complete primary outcome measures (Table 1). To assess comfort eating, participants will take part in a well-validated faux taste test from previous research (described below).¹⁰² To provide a measure of social avoidance/withdrawal, we will use a previously validated measure⁵⁰ in which participants indicate the extent to which they prefer to complete the final task either by themselves, with a member of their previous group, or with a new partner (described below). Anthropometric measures (i.e., height, weight, waist and hip circumference) will be assessed at the end of the study following standard lab-based procedures.

To assess cortisol (a steroid hormone that regulates the body's response to stress), participants will be asked to provide three saliva samples during the lab visit. The first saliva sample will be collected at baseline (5-10 minutes after they arrive at the lab). The second and third saliva samples will be collected 25 and 60 minutes, respectively, after delivery of the experimental manipulation. If participants finish all study measures before it is time to collect the third saliva sample, they will be asked to watch a video about marketing strategies to presumably help them prepare for the final task. Here's a link to the kind of video that will be shown to participants:

https://www.youtube.com/watch?v=0Ty64auIk_w

The experimenter will be instructed to stop the video when it's time to collect the sample.

We will use off-the-shelf foods for the taste test task. The following foods/drinks will be offered to participants: Lay's classic potato chips, Chips Ahoy cookies, milk chocolate M&M candies, and Sprite. During the taste test, participants will be provided with plentiful quantities of each food item (i.e., 80 grams of chips, 15 cookies, 300 grams of M&Ms) and 2 (355 mL) can of Sprite. These quantities were selected to circumvent both ceiling effects (i.e., participants eating all of the food available) and floor effects (i.e., participants eating no food at all) and are currently being used in a similar study being conducted by Co-I, [name]. All food items will be stored according to package instructions (e.g., in airtight containers to preserve freshness). Cans of Sprite will be refrigerated. Participants will not be given food items that have become stale or are beyond their "best by" date. Any expired foods will be discarded. For sanitary reasons, any food or drink that is leftover after the taste test will be discarded as soon as the research assistant has logged the post-task weight for each item.

Participants will be screened for relevant food allergies on the screening survey (see attached). Those individuals who report being allergic to one or more of the products on the list will be excluded from the study. To take additional precautions, the consent form will remind participants of the food tasting and rating task that will take place during the lab visit. Participants will be instructed to alert a member of the study team if they have a relevant food allergy. If this occurs, the participant will be informed that they do not meet the eligibility criteria for the study and thus will not be scheduled for the lab visit (i.e., they will be withdrawn from the study for not meeting eligibility criteria). Further,

PROTOCOL TITLE: Decision Making Study

immediately prior to the food tasting exercise, the experimenter will remind participants of the ingredients contained in the foods they will be tasting. Participants will again be queried as to whether they have any relevant food allergies. If a participant admits to having a food allergy, any food items containing the specified ingredient(s) will not be offered to the participant during the taste test. In the unlikely event that a participant is allergic to all of the items of the food allergy list, the food tasting exercise will not be conducted.

The experimenter will bring the food to the lab room on a tray and will wear gloves while handling the food and presenting it to the participant. After setting down the tray, the experimenter will open a can of Sprite in front of the participant. To introduce the task the experimenter will say the following:

“Okay, now it’s time for the food tasting and rating task. These are the same foods that you’ll be promoting in your food marketing campaign, so we wanted to give you a chance to try them. Please have at least a taste of each item so that you can rate them. Rate the foods using this form [hand participant food rating form; see attached food rating form]. You are welcome to have as much as want. It is important that you answer the questions on the form as accurately as you can, so if you need more food to answer the questions, please let me know. [Add off-handedly] And if you finish early, feel free to eat as much as you want. For sanitation purposes, we have to throw it away after you go anyway. You’ll have about 10 minutes for this task. If you finish before I return, please feel free to review your ratings to make sure they are accurate.”

To assess social avoidance/withdrawal, the experimenter will say the following after the participant has completed the food tasting task:

“Next, you’ll be sharing your ideas for the food marketing campaign. There are a few ways we can do it and it’s up to you. You can do it by yourself, you can do it with one of the remaining people from your previous group—the same people in the videos you watched earlier—or there’s someone else who showed up late for the study and you could do it with them. You haven’t met them yet, but they’ll be doing the marketing task as well so that’s another option. Just so you know, the task will take the same amount of time whether you do it by yourself or with another person.

So again, your options are by yourself, with a former group member, or with the new group member who showed up late. Please give it some thought. I’ll be back in a few minutes and you can let me know your preference then.”

Participants will be asked to indicate their response verbally to the experimenter, who will record their response.

Describe procedures performed to lessen the probability or magnitude of risks and source records

Our team is highly committed to the protection of participant welfare. We will work closely with our university’s Institutional Review Board to ensure participant wellbeing and safety. Further, we will follow best practices for debriefing all study participants.

We will follow best practices for saliva sample collection. For example, participants will receive verbal instructions from the experimenter along with a written handout that

PROTOCOL TITLE: Decision Making Study

repeats the instructions and provides additional tips if they are having difficulty producing enough saliva (please see attached). Participants will also be given privacy and as much time as needed to provide the sample.

All participants will undergo a “funneled” debriefing process at the end of the study that begins with broad questions that narrow to probe for suspicion. The debriefing process will consist of an initial verbal debriefing with the research assistant, followed by receipt of a written debriefing form that provides additional information and psychological support resources. After receiving this information, participants will have the opportunity to discuss the study with the research assistant and ask questions. Here, we provide a brief summary of the verbal debriefing process and the information contained in the written debriefing form.

Debriefing Procedure Summary: The research assistant will begin by asking the participant a series of questions to assess prior knowledge of any aspects of the study (e.g., “Did anyone else tell you anything about what you would be doing in this study before your session today?”) and gauge suspicion about study procedures (e.g., What do you think today’s study was about? Was there anything we told you during the study that you didn’t believe?”). Afterwards, the research assistant will explain the goals of the study and the nature of the two experimental conditions. All aspects of the procedure, including all elements of deception, will be explained clearly to participants. Participants will be assured that any feedback they received during the session from their ostensible partners was not real (i.e., the GTKY and first impression ratings from their “co-workers,” being told that no one wanted to work with them on the partner task) and was developed by the research team to elicit particular types of reactions. Research assistants will emphasize this point until they are confident participants understand that none of the study procedures reflect any actual evaluation of the participant. The research assistant will apologize for not initially disclosing the purpose of the study and apologize for any discomfort that may have been experienced while completing the study measures or tasks.

Research assistants will be trained on how to assist participants who experience distress. Further, participants will be given a list of psychological support resources they can utilize (e.g., helplines) if they experience any lingering distress after the study has ended. Upon receiving full disclosure of the study goals, participants will be given the opportunity to withdraw their data from the study.

Participants will be thanked for their participation and given the written debriefing form. The debriefing form will provide a more detailed version of the verbal debriefing by outlining the study purpose and rationale underlying the current study. After receiving the verbal and written debriefing, participants will be given an opportunity to discuss the study with the research assistant and ask questions about the procedures and study goals. Participants will also be provided with several suggested readings if they are interested in learning more about weight discrimination and health, efforts that will be taken to protect their confidentiality, and a list of psychological support resources. The form will include contact information for the PI ([name]) and the FSU human subjects committee should participants have any additional questions or concerns about the study.

Participants will be instructed to contact the PI if they would like to receive a copy of the

PROTOCOL TITLE: Decision Making Study

study results.

Source Records: Please see attached documents for all surveys that will be used to collect data about participants (i.e., screening survey, baseline survey, lab survey).

Describe what data will be collected during the study and how that data will be obtained.

Outcome measures include cognitive (self-regulation); affective (emotional states); behavioral (social withdrawal, comfort eating); and physiological (cortisol secretion as indicated via saliva) responses to experimentally manipulated weight discrimination. Measures will be assessed with experimenter-administered and self-administered survey questions, computer-based tasks, a saliva sample, and a faux taste test. Please see previous description of outcomes for more detail.

Proposed psychological and demographic moderating variables will be assessed in the screening survey and baseline survey.

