Psychological moderators. Further, participants high in internalized weight bias (IWB) and neuroticism were more likely to view the negative feedback as reflecting weight discrimination and to report more negative emotions, whereas participants high in self-compassion and conscientiousness demonstrated the opposite pattern. Findings support Aim 1 by demonstrating effects of weight discrimination on negative emotions and self-regulation and Aim 2 by identifying psychological moderators.

Pilot Study 3: Cognitive, Affective, and Behavioral Correlates of Expectations of Rejection. This lab study identified individual differences associated with expectations of rejection during a novel social interaction and the implications of those expectations for psychological and behavioral outcomes. Before completing a task with a partner (a member of the study team), adults with obesity (N=111) reported the extent to which they thought they would be accepted vs. rejected by their partner. Participants who anticipated rejection by their partner reported more distress and anxiety. Expectations of rejection were also associated with social withdrawal, indicated by participants choosing to work by themselves to avoid further social interaction.

Psychological moderators. Participants high in internalized weight bias and neuroticism reported higher expectations of rejection, more distress and anxiety, and greater social withdrawal. In contrast, participants high in self-compassion demonstrated the opposite pattern. These findings demonstrate support for Aim 2.

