Social withdrawal. Social withdrawal will be assessed with a measure from previous research,⁵⁰ in which participants indicate the extent to which they want to work on a task either by themselves, with one of their former group members, or with a new partner. Choosing to work by oneself reflects a desire to avoid social interaction. The details of the task will be tailored for the study to fit the study's narrative flow.

Comfort eating. Comfort eating will be assessed via an eating task to objectively measure hyperpalatable (high-fat, -sodium, -sugar, and -carbohydrate) food intake.¹⁰¹ To avoid floor effects often observed in laboratory eating settings, the eating task will take place under the guise of a faux taste test.¹⁰² Participants will be asked to rate each of the

PROTOCOL TITLE: Decision Making Study

foods/drinks to ostensibly guide the development of their food marketing campaign later during the study. To avoid ceiling effects and to allow participants to eat without fearing that the experimenter will negatively judge the amount they have eaten, large quantities of each food will be made available. Participants will have 10 minutes to complete the task alone in a private room. Bowls will be weighed (unobtrusively) before and after the task to compute the difference in grams, which will then be converted to kilocalories based on published nutrition information from the food maker.

Self-efficacy for weight control behavior. Self-efficacy (perceived confidence) in one's ability to engage in weight control behaviors (e.g., dietary restraint, physical activity) over the next six months will be assessed with items adapted from previous research. Self-efficacy for dietary restraint will be assessed with the short form of the Weight Efficacy Lifestyle Questionnaire¹⁰³ (e.g., I can resist eating ... when I am depressed or down; 8 items). Self-efficacy for physical activity will be assessed with the Exercise Self-efficacy Scale¹⁰⁴ (e.g., I am confident I can participate in regular exercise when ... I am tired; 5 items). To mask the study's focus, weight control items will be interspersed with items assessing self-efficacy for other health behaviors (e.g., flu vaccination, sleep, cancer screening). Participants will rate their self-efficacy for each behavior on an 8-point scale (0=not at all confident to 7=very confident). Items will be averaged to create a composite score.

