17.0 Data Management and Confidentiality

Statistical Design, Power, and Analysis Plan

We designed this study to have very high power for the main effects of weight discrimination (Aim 1) and to ensure sufficient sensitivity for moderation effects of psychological (Aim 2) and demographic variables (Aim 3).

➤ **Aim 1: Identify early-stage cognitive, affective, behavioral, and physiological mechanisms activated by experimentally manipulated weight discrimination.** We hypothesize that, relative to participants in the control condition(s), participants in the weight discrimination (experimental) condition (vs. control) will display more impaired self-regulation, higher negative emotion, lower positive emotion, more social withdrawal and comfort eating, lower self-efficacy and intentions for engaging in weight control behavior, and increased cortisol secretion.

Aim 1 power and analysis. Nine outcomes are assessed for the study (Table 1), hence we adopt a conservative Bonferroni adjustment when evaluating the primary hypothesis and use significance level $\alpha = 0.005$ to maintain familywise Type I error rate of 0.05. We assumed conservative effect size estimates, which were among the smallest observed in our pilot data.⁴⁸ We plan to recruit 160 subjects per condition for the study, which yields 90% power ($\alpha = 0.005$) to detect the medium Cohen's $d = 0.50$ between the control and experimental conditions.

Aim 1 analyses will use unadjusted ANOVA followed by analysis of covariance and multiple regression methods that permit adjustment for age and other baseline characteristics that may exhibit imbalance across experimental conditions. To analyze effects of the manipulation on cortisol secretion (assessed at 3 timepoints), we will calculate the area under the curve (AUC) with respect to ground (AUCg).¹²⁰ For all Aims, residual diagnostics will assess model assumptions (e.g., normality, homogeneity) and responses will be transformed if necessary. Effect of experimental weight discrimination will be reported for both unadjusted and adjusted analyses.

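### Social withdrawal is described as a graded rating but scripted as one spoken choice; scored alone vs not alone, Section 17.0's Aim 2 power figure does not apply to it and ordinary standard errors are unreliable

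*Combined protocol and SAP*

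**What the plan says.** **Graded wording.** Section 4.0 says "participants indicate the extent to which they want to work on a task either by themselves, with one of their former group members"; a third option, somebody they have not yet met, completes the list. The procedural summary in Section 6.0 repeats this: "participants indicate the extent to which they prefer to complete the final task either by themselves", and so on through the other two options.

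**Choice wording.** The script later in Section 6.0 offers the options once: "your options are by yourself, with a former group member, or with the new group member who showed up late". It continues: "Participants will be asked to indicate their response verbally to the experimenter, who will record their response". No rating scale is mentioned. Section 4.0 itself moves to a choice: "Choosing to work by oneself reflects a desire to avoid social interaction". Section 3.0 describes withdrawal in Pilot Study 3 as "indicated by participants choosing to work by themselves to avoid further social interaction".

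**Analysis.** Section 17.0 lists more social withdrawal among the nine Aim 1 hypotheses without naming a variable or coding. "Aim 1 analyses will use unadjusted ANOVA followed by analysis of covariance and multiple regression methods". Aim 2 tests a condition-by-moderator interaction in multiple regression. Section 17.0 treats no moderation as the same thing as equal correlations in the two arms. It gives 90% [80%] power, two-sided 0.05, for correlations of 0.65 vs 0.39 [0.43] with 160 per arm.

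**The concern.** A rating and a single choice produce different variables, and one of nine Bonferroni-tested outcomes is left open between them. If the choice is what is collected, alone vs not alone is the reading the text favours. Its standard deviation is then fixed by the proportion choosing alone, and Aim 1 predicts that this proportion differs by arm.

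Two things follow for Aim 2. The stated power comes from a comparison of correlations, whereas the planned test compares slopes, so the figure need not describe that test. And the residual variance of a 0/1 outcome changes with the moderator, so ordinary least-squares (OLS) standard errors for the interaction can be too small or too large. What is at stake is the error rate and the stated sensitivity of the moderation test for this outcome.

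**Working it through.** **Inputs.** From Section 17.0: 160 per arm; Aim 1 alpha 0.005 (taken as two-sided); Aim 2 alpha 0.05 two-sided; correlations 0.65 vs 0.39 [0.43]. Assumptions, because the plan gives no choice rates: control proportion choosing alone 5% to 50%; a normal moderator with SD 1; and, in simulations, a threshold model for the choice.

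**1. The plan's own figure.** Fisher z, SE = sqrt(2/157) = 0.1129.
- 0.65 vs 0.39: (0.7753 - 0.4118)/0.1129 = 3.22; power = Phi(3.22 - 1.96) = 89.6%.
- 0.65 vs 0.43: (0.7753 - 0.4599)/0.1129 = 2.79; power = 79.8%.

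Both reproduce. The question is whether they transfer to this outcome.

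**2. Aim 1 on the 0/1 score.** Two-proportion z test, 160 per arm, alpha 0.005:

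| Control rate | 5% | 10% | 20% | 30% | 40% | 50% |
|---|---|---|---|---|---|---|
| Experimental rate for 90% power | 20.0% | 27.7% | 40.9% | 52.3% | 62.7% | 72.1% |
| Difference (points) | 15.0 | 17.7 | 20.9 | 22.3 | 22.7 | 22.1 |

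A difference equal to d = 0.50 on the 0/1 score has 94% power throughout, above the 90% that Section 17.0 states for d = 0.50. The simulated size of the ANOVA is 0.0037 to 0.0052 against 0.005. Aim 1 is sound on this reading.

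**3. Power of the planned interaction test.** With moderator SD 1, slope = r × SD(outcome), and for a 0/1 score SD = sqrt(p(1 - p)). The test statistic is approximately (r1·s1 - r0·s0) / sqrt{[s0²(1 - r0²) + s1²(1 - r1²)]/160}.

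Example: 20% in controls and 40.9% in the experimental arm, so s0 = 0.400 and s1 = 0.492.
- Larger correlation in the experimental arm: slopes 0.156 and 0.320, SE 0.041, power about 98%.
- Larger correlation in controls: slopes 0.260 and 0.192, SE 0.043, power about 35%.

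Simulation, OLS interaction, arms differing by the amounts in step 2:

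| Control rate | 15% | 20% | 30% | 40% | 50% |
|---|---|---|---|---|---|
| 0.65 experimental, 0.39 control | 99% | 99% | 94% | 81% | 57% |
| 0.65 control, 0.39 experimental | 20% | 33% | 64% | 86% | 96% |

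For comparison, a continuous outcome with equal SDs gives 0.26 / sqrt[(0.5775 + 0.8479)/160] = 2.75, or about 79% power. Simulation gives about 78% [64%].

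**4. Error rate with truly equal slopes.** Threshold model, correlation 0.39 in controls, nominal 5%:

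| Control rate | 5% | 10% | 30-50% |
|---|---|---|---|
| OLS, same rate in both arms | 24% | 13% | about 2-4% |
| OLS, arms differing as in step 2 | 10% | 6.5% | about 2-4% |

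HC3 gives 4-6%. When few choose alone, the outcome variance is largest at one extreme of the moderator, where observations carry most leverage, so OLS understates the error. Near 50% the variance is smallest at the extremes, and OLS overstates it.

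**5. Sensitivity stated as a difference in slopes.** Detectable difference = (1.96 + z_power) × sqrt[(p0q0 + p1q1)/160], in points per moderator SD. At 20% and 40.9%: 2.80 × sqrt(0.4016/160) = 14.0 points at 80% power. It uses total rather than residual variance, so it is approximate.

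| Control rate | 5% | 10% | 20% | 30% | 40% | 50% |
|---|---|---|---|---|---|---|
| Arms differ as in step 2: 80% power | 10.1 | 11.9 | 14.0 | 15.0 | 15.2 | 14.9 |
| Same: 90% power | 11.7 | 13.8 | 16.2 | 17.4 | 17.6 | 17.2 |
| Equal rates: 80% power | 6.8 | 9.4 | 12.5 | 14.4 | 15.3 | 15.7 |
| Equal rates: 90% power | 7.9 | 10.9 | 14.5 | 16.6 | 17.8 | 18.1 |

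**The case against.** **The text largely resolves itself.** Section 4.0 interprets the measure as a choice, Pilot Study 3 did the same, and the script is the operational text. The attached lab survey and the cited source of the measure were not available and may hold a graded item. This stands as a reason to treat the conflict as one to reconcile rather than to presume an answer. Section 17.0 would still need to name the tested variable.

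**The low-power row should not be the headline.** A reader might infer that moderation power for this outcome is as low as 20% or 33%. The documents do not support that. Aim 2 predicts stronger effects at higher internalized weight bias and neuroticism, and weaker ones at higher self-compassion. With the directions seen in Pilot Study 3, that puts the larger correlation in the experimental arm, where power is 99% at control rates of 15-20%. The 20% and 33% cases also need latent correlations of about 0.995 and 0.93, so that the trait almost determines the choice. Section 17.0's phrasing of the change can be read in either direction, so the low-power row is possible but not favoured.

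**The equal-correlation premise is a wider matter.** It fails for any outcome whose SD differs by arm. Even with equal SDs the interaction test has about 78% [64%], not 90% [80%]. That objection stands. Only the dependence on choice rate and the standard-error problem are particular to a 0/1 score.

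**The transformation rule.** Section 17.0 says "residual diagnostics will assess model assumptions (e.g., normality, homogeneity) and responses will be transformed if necessary". A reader might infer that this undermines the analysis, because recoding two values changes nothing. No consequence follows: the ANOVA size in step 2 is already close to nominal.

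**Conclusion.** The concern holds as a minor point. The documents describe two response formats and declare no tested variable. If the outcome is alone vs not alone, Aim 1 works as planned. For Aim 2, the 90% [80%] figure is correct arithmetic for a different test. With the larger correlation in the experimental arm, the planned test has about 99% to 57% power over assumed control rates of 15% to 50%. OLS standard errors give about 2% to 24% rejection under truly equal slopes over assumed control rates of 5% to 50%, against 4-6% with HC3.

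These sizes rest on assumed choice rates, a normal moderator and a threshold model. The worst inflation needs only about 5% choosing alone in both arms; at 30-50% the OLS test is conservative instead. The documents support neither a general claim that Aim 2 is underpowered for this outcome nor any claim of an Aim 1 shortfall.

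**What to change.** 1. Reconcile the graded descriptions in Sections 4.0 and 6.0 with the scripted choice. If the lab survey holds a graded rating that is meant as the outcome, say so in the Section 6.0 script and in Section 17.0 instead.
2. If the choice is the outcome, declare alone vs not alone in Section 17.0 as the tested variable and report the three-way split descriptively.
3. Keep the planned linear model, with its difference-in-slopes definition of moderation, and use HC3 standard errors for this outcome.
4. State that the correlation-based Aim 2 power does not apply to it. If a sensitivity is given, express it as a difference in slopes with both arms' assumed rates stated. Over control rates of 5-50%, this is about 10-15 points per moderator SD at 80% power (12-18 at 90%) when the arms differ by the Aim 1 90%-power amounts, and about 7-16 (8-18) when the rates are equal.

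The cost is wording and one standard-error option, with no new item, script change or added participants if the choice is the outcome. The downside is that the stated Aim 2 sensitivity for this outcome becomes conditional on assumed rates.
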